**Preventing Postpartum Depression: A Dyadic Approach Adjunctive to Obstetric Care**

**NCT03283254**

**November 12, 2024**

## **STUDY PROTOCOL**

### **CONSENT:**

Consent is obtained by those study staff with a Bachelor's degree or higher, who passed all necessary CITI training, and are IRB-approved to obtain consent. A link to the consent form is sent to the participant prior to the consent session. Consent forms are either signed in-person on paper copies or are signed electronically via REDCap by both the potential participant and the research staff obtaining consent. Potential participants are emailed the link to the electronic consent form prior to the virtual consent session, which they can access with any device that can connect to the internet. The Redcap consenting record is updated to contain the most recent IRB-approved and stamped Consent and HIPAA forms. All potential participants are asked if they give additional, optional consent to have their participation in the study filmed for use in front of a professional audience. If participants give consent to be filmed, they are provided with an additional consent form addendum. An informed Consent Form is sent via an alert which is logged, time-stamped & encrypted when the "protect mode" is turned on. The risks related to a loss of confidentiality when using electronic devices to transmit, store, and/or access the Consent Form and HIPAA forms are outlined in the Consent Form and discussed during the consent process. Additionally, the possibility that data could be accessed by others, should the participant lose their electronic device, lend the device to other people, or if the device is subject to a search warrant or subpoena, is described to the participant during the consenting session. All participants who sign via REDCap, are offered the option to receive the consent and HIPAA forms as hard copies via the mail if requested.

## **SCREENING**

### **PHASE 1 OF SCREENING**

Phase 1 of screening is conducted via telephone by a CITI trained research assistant to determine if participants meet the initial inclusion and exclusion criteria listed below. The results are entered in REDCap, an online secure database. All information entered in Redcap is de-identified using a screen ID. Any identifying information is entered in a password-protected Excel document on our server.

Inclusion and Exclusion Criteria: Participants are screened at 20-29 weeks gestation

Inclusion:

1. Healthy pregnant women between 18-45 years old [phone screen, self report]:
2. A healthy, singleton pregnancy [phone screen, self report]
3. Fluent English speaker [phone screen, self report]
4. Receiving standard prenatal care [phone screen, self report]
5. A score of 19 or greater on the Predictive Index of Postnatal Depression (PIPD), indicating risk for developing postpartum depression; or score of 7 or greater on the Edinburgh Postnatal Depression Scale (EPDS). [phone screen, assessment administered by trained staff]

Exclusion:

1. Multi-fetal pregnancy [phone screen, self report]
2. Illicit drug use, alcohol use during pregnancy [phone screen, self report]
3. Acute medical illness or significant pregnancy complication [phone screen, self report]
4. Currently in weekly, individual psychotherapy, including psychopharmacology [phone screen, self report]
5. Psychotic d/o; Bipolar I; Major Depressive Disorder [phone screen, MINI assessment and clinical interview administered by trained clinicians] (Determined in Phase 2 of Screening)

If eligible based on the initial phone screen, participants are asked to participate in a follow-up screening session, either by telephone or via HIPAA compliant video call to assess the final IRB approved exclusion Criteria (which are determined by the clinical interview and MINI assessment, which is administered by a licensed clinician or an unlicensed clinician under licensed supervision.

## **PHASE 2 OF SCREENING**

The potential participant is first consented for this screening session. If consented, the potential participant undergoes a screening conducted by both the research assistant and a licensed clinician or an unlicensed clinician under licensed supervision.

The potential participant then meets virtually with a licensed clinician or an unlicensed clinician under licensed supervision who conducts a clinical interview and a standardized assessment

(MINI) to screen for psychosis, major depressive disorder, and bipolar disorder. Participants that meet criteria for any of those disorders are not enrolled in the study, but the clinician is to proceed by: (1) making an immediate appropriate referral, or (2) arranging for an immediate psychiatric evaluation.

Information collected during the screening procedure was used to confirm eligibility based on the IRB approved inclusion and exclusion criteria. The screening and the screening results were reviewed and approved by the PI.

#### **Baseline Assessment (20-29 weeks gestation):**

A trained research worker will administer the Hamilton Anxiety Scale (HAM-A) and Hamilton Depression Scale (HAM-D) to the participant.

#### **Prenatal Session 1 (28-32 weeks gestation)**

At this time point, if the individual agrees to participate in this session and gives consent, the individual is randomly assigned to one of two groups: Intervention vs. Enhanced Treatment As Usual (ETAU). When the participants are 28-32 weeks pregnant, they participate in an in-person session (pre-COVID) or in a virtual session (during COVID), either by phone or video call, and are asked to complete mood assessments, a cognitive assessments and answer questionnaires about feelings, life events, and sleep. Participants are asked a questionnaire about the effect of COVID-19 on their lives. In total, these questionnaires take about 90 minutes. All questionnaire results are entered in Redcap, an online secure database. All information entered in REDCap is de-identified using a screen ID. At home, we ask participants to wear an activity monitor for 7 full 24-hour days. We ask participants to complete a sleep diary noting sleep times and durations for the seven consecutive days they are wearing the activity monitor.

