#### **Prenatal Session 2 (34-39 weeks)**

At 34-39 weeks gestation, participants have another session (in-person if pre-COVID or virtual if during COVID), and complete mood assessments, a cognitive assessment, and answer more questions about feelings and sleep. This session takes about 75 minutes. They are asked to wear the activity monitor again for 7 days and complete a sleep diary (5-10 minutes to complete).

All participants are provided with psychoeducation (and an information sheet) that highlights the warning signs of depression and the risks of depression and contact information for research staff so that they can access help and referrals if they begin to experience depression. All participants (regardless of group assignment) are encouraged to contact the study clinician at any point during the study if they are interested in a referral for treatment.

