## **6-Week Postpartum Session**

At 6 weeks postpartum, participants are asked to participate in another session (in-person if pre-COVID or virtual if during COVID), to complete mood assessments. This session is about an hour. During this session, participants are videotaped as they engage in a standard routine of infant care. This takes about 5 minutes to complete.

If the session is completed in-person (not virtually), participants are invited to complete the infant EEG. We will examine variation in EEG left/right power asymmetry in relation to potential group differences in the effectiveness of the intervention in helping mothers function as a social "buffer" and modulate infant reactivity. The 6-week postpartum EEG sleep protocol takes place while the baby is sleeping. This is a non-clinical EEG recording. A cap with EEG sensors is placed on the newborn's head by a trained member of the research team. The research team then waits for the baby to enter a state of quiet sleep. This allows the research team time to measure brain activity while the baby sleeps. The participant is reassured by the research team that although the sensors might leave a red mark briefly after they are removed, this procedure is completely painless and does not harm the newborn.

The EEG session takes approximately 30 minutes. This session is video recorded to allow the researchers to collect information about infant behavior during the session. In total, including setup of materials and video-recording, the 6-week EEG session is approximately 1.5 hours in duration.

The participant is allowed extra time to pick up, feed, comfort, or change the infant to accommodate fussiness or discomfort at any time during the EEG. If the participant is uncomfortable with the EEG, they are free to stop the session.

Participants wear an activity monitor again for 7 full days. While wearing the monitors, participants complete a sleep diary noting sleep times and durations, which takes about 5-10 minutes. Participants in the treatment group are asked to complete a diary entry that asks them the frequency and duration of their utilization of the skills learned from PREPP (i.e., carrying/holding baby, accentuation of day/night cues, focal feeding, use of swaddling,

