### **12-Week Phone Session**

At 12 weeks postpartum, participants complete mood assessments over the phone. This takes about an hour to complete.

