### **16-Week Postpartum Session**

At 16 weeks postpartum, participants are asked to participate in a final session (in-person if pre-COVID or virtual if during COVID) to complete mood assessments and other questions related to feelings, life events, and sleep. Participants are asked again to complete a questionnaire about the effect of COVID-19 on their lives (if during COVID pandemic).

All together, these questionnaires take an hour to complete. Participants are asked to sit on the floor and play with their baby using a set of toys they usually use at home. They are asked to engage in free play for 10 minutes, and their play interaction is videorecorded and later coded using the Emotional Availability (EA) Scales. Mothers and infants are also asked to participate in a modified 'double' Still Face Protocol (SFP), an A-B-A-B-A design with alternating free-play (A) and still-face (B) periods. The entire SFP session is videotaped for later behavioral coding. The session begins with five minutes of face-to-face free play, followed by a two-minute still-face episode. Two additional free-play periods and a second still-face episode, each lasting two minutes, follows. A study coordinator signals transitions by saying "Switch". If the infant cries for more than 30 seconds or intensely for over five seconds, the session is stopped so the mother can comfort the infant. The full procedure lasts about 20 minutes. Frequency of infant positive affect, signs of avoidance (infant head turn and back arch), and duration of infant distress/crying and neutral/positive vocalizations will be coded. Mothers will be coded for duration of vocalizations to the infant, touching the infant, and positive/negative affect.

During this session, participants are also videotaped as they engage in a standard routine of infant care. This takes about 5 minutes to complete.

For a final time, participants wear the activity monitor again for 7 days. Participants complete a sleep diary noting sleep times and durations, which takes them 5-10 minutes to complete.

Participants in the treatment group complete a diary entry asking them about the frequency and duration of their utilization of PREPP skills. Infant sleep is assessed using a Smart Sleep Sensor worn by the infant. The Sensor detects day and night sleep activity by recording activity patterns during the time intervals in which it is worn. Infants wear the Sensor for four days (24- hour periods).

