### Treatment Protocols:

#### Experimental Arm: PREPP Intervention

The intervention is carried out at 5 timepoints, Session 1 at 28-32 gestational weeks, Session 2 at 34-39 gestational weeks, Session 3 at 6 weeks postpartum, Check-In Session 1 within 3 days of the birth and at Check 2 Session at 2 weeks postpartum. These sessions are scheduled to coincide with standard medical visits (3rd trimester ultrasounds and 6-Week Well Baby visit), which enable us to test the feasibility of incorporating these sessions into routine medical care. A licensed trained clinician or an unlicensed trained clinician under licensed supervision provide the intervention. The sessions of this preventive psychotherapy are comprised of three

components: (a) mindfulness and self-reflection skills, (b) parenting skills and (c)psycho-education. The intervention protocol encompasses the following 5 specific established behavioral techniques: (1) feeding the infant between 10 pm and midnight, even if s/he must be awakened ('a focal feed'); (2) accentuating differences between day and night cues so that there are higher levels of stimulation during the former than the latter; (3) assuming adequate weight gain is reached by 3 weeks, lengthening the latency to feeding time in the middle of the night by engaging in other attentive activities such as walking with the baby and diapering; the goal is to lengthen the nighttime feeding intervals by extinguishing the association between night time waking and feeding; (4) carrying infants for a minimum of 3 hours a day, throughout the day, independent of responding to crying, carrying during feeding, and whether the baby is awake; and (5) learning to swaddle the baby as a possible soothing intervention. Mindfulness-based tools are provided with the aim to (1) aid them to return to sleep after waking at night, (2) help them to cope better when their babies are distressed or unsoothable. These mindfulness exercises are provided as audio files via an App.

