#### **Statistical Analysis Plan**

**Overall.** Based on preliminary data, we anticipate minimal attrition ( $\leq 5\%$ ) during the first two assessment sessions (pre-delivery), and up to 33% attrition postpartum across both groups in the worst-case scenario. All participants with data available for a given study phase (pre- or postpartum) will be included in the primary analyses. Before conducting hypothesis tests, we will screen all variables at all time points for out-of-range values, outliers, and data inconsistencies. Means, standard deviations, interquartile range, minima, and maxima for continuous variables and proportions for categorical variables will be reported.

Following CONSORT guidelines, the primary analyses for all aims will follow an intention-to-treat (ITT) approach, including all randomized participants regardless of treatment adherence or dropout. If significant imbalances in baseline covariates (e.g., maternal age, BMI, birth order, infant sex) are observed despite randomization, these variables will be included as covariates in the models. Additional exploratory models will examine relevant biological factors, such as maternal BMI, fetal/infant sex, maternal age, infant gestational age at birth, and birthweight corrected for birth age, as potential covariates.

**Aim 1.** Reduce women's distress during pregnancy. We hypothesize that PREPP will be associated with: (A) Diminished depressive symptoms using interviewer-rated and self-report questionnaires; (B) Improved perception of sleep quality relative to objective changes in sleep duration (per self report and actigraphy).

**Analysis for Aim 1A:** For depressive symptom outcomes (HRSD, PHQ-9, HRSA, PSQI, EPDS), we will fit linear mixed-effects models with fixed effects for Treatment (PREPP vs. ETau), Time (2nd and 3rd assessments), and birth order, along with subject-specific random intercepts. For EPDS, we will adjust for the screening score and test a Treatment  $\times$  Screening Score interaction as a secondary analysis. Additional moderators will also be tested.

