**Analysis for Aim 1B:** Two ActiGraph-derived measures, total sleep time (TSTact) and sleep efficiency (SEact), will serve as outcomes in separate mixed-effects models with fixed effects for time and day (within the ActiGraph epoch) and subject-specific random intercepts, assuming an AR(1) correlation structure. We will assess whether adjustment for weekday/weekend is warranted. Subject-specific means of these measures will be used as predictors of their subjective

counterparts (TSTact, SEact) in additional mixed models testing for treatment group differences in the association between objective and subjective sleep measures. Moderation by trauma history and attachment will be explored.

**Aim 2. Determine the maintenance of improved maternal mood and differences in infant behavior.** We hypothesize that PREPP will be associated with: (A) Lower rates of PPD and distress, including poor sleep efficiency, assessed by interviewer-rated and self-report questionnaires as well as sleep actigraphy. (B) Less infant fuss/cry behavior and longer nocturnal sleep bouts based on maternal report and actigraphy.

**Analysis for Aim 2A:** Separate linear mixed-effects models will be used for each maternal mood outcome (PHQ-9, HRSD, EPDS, HRSA, PSQI) and ActiGraph-derived sleep measures. Models will include Treatment, Time (6, 12, and 16 weeks postpartum), and their interaction, with baseline (pregnancy) values as covariates. Subject-specific random intercepts will be included. The primary parameter of interest is the Treatment  $\times$  Time interaction; if non-significant, the main effect of Treatment will be tested. PPD diagnosis will be modeled using mixed-effects logistic regression with analogous fixed effects.

For infant outcomes (6 and 16 weeks), linear mixed-effects models will assess Treatment effects without Time  $\times$  Treatment interaction. Sleep data will be processed as in Aim 1B. Covariates include time-varying factors such as weaning, solid food introduction, maternal return to work, and social support. Moderators (infant sex, trauma history, attachment) will also be assessed.

**Analysis for Aim 2B:** Infant sleep and cry behavior at 6 and 16 weeks will be compared using mixed-effects models with Treatment, Time, and their interaction as fixed effects. Covariates and secondary analyses will be same as those in Aim 2A.

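### Most sessions moved from in-person to virtual with COVID, yet no Aim 1 or Aim 2 model adjusts for period and no by-period result is planned: a small, avoidable loss of precision, mainly in Aim 1

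*Combined protocol and SAP*

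**What the plan says.** **Session mode.** Prenatal Session 1, where randomisation takes place, is described as an "in-person session (pre-COVID) or in a virtual session (during COVID), either by phone or video call". Prenatal Session 2 and the 16-Week Postpartum Session carry the same rule. At 6 weeks, "participants are asked to participate in another session (in-person if pre-COVID or virtual if during COVID), to complete mood assessments". The 12-week visit does not switch: "At 12 weeks postpartum, participants complete mood assessments over the phone".

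**COVID data.** A COVID-19 questionnaire is scheduled at the first prenatal visit and at week 16. No Aim 1 or Aim 2 model names it.

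**Models (Statistical Analysis Plan).**
- Aim 1A has "fixed effects for Treatment (PREPP vs. ETau), Time (2nd and 3rd assessments), and birth order", with random intercepts. Only EPDS has a stated adjustment for its screening score.
- Aim 1B lists time and day within the recording.
- Aim 2A: "Models will include Treatment, Time (6, 12, and 16 weeks postpartum), and their interaction", with pregnancy values as covariates and random intercepts. The interaction is the primary parameter.
- Aim 2B has Treatment, Time and their interaction, with covariates as in Aim 2A (weaning, solid food, return to work, social support).

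The Overall paragraph adds covariates if baseline imbalance is significant. It also lists exploratory biological covariates. Aim 1A promises further moderators without naming them. Period and session mode appear nowhere.

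**The concern.** The conditions of assessment changed part-way through the trial, and the date of each visit shows which side of the change it falls on. Period is practically unaffected by the assigned arm, so adjusting for it is safe. If mood or sleep differed between periods, leaving the term out puts that difference into the error. Women who were randomised before COVID and seen later during it would add within-person variation that the models can only assign to Time and residual error.

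The existing clauses do not cover this. The imbalance rule responds to significant baseline imbalance, not to precision, and it cannot handle a factor that changes between a woman's visits.

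What is at stake is some power, and openness about what was pooled. As planned, a reader will see neither how many women in each arm fell in each period nor whether the estimates look similar.

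**Working it through.** **Inputs from the Power analysis paragraph.** N = 214 (107 per arm), 5% attrition in Aim 1, threshold 0.05/5 = 0.01. Two-sided testing and 80% power for Aim 1 are assumed; the paragraph states 80% only for Aim 2.

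**Inputs not in the documents.** The share p of women in the COVID period and the mean shift s between periods (in within-period SDs) are assumptions, shown as ranges.

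**1. The plan's Aim 1 figure.** n = 214 × 0.95 / 2 = 101.65 per arm. Detectable d = (2.576 + 0.842) × √(2/101.65) = 0.479, against the stated 0.48. It reproduces as a single-visit comparison; the stated within-subject correlation of 0.2 plays no part in it.

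**2. Value of a period term in Aim 1, single visit.** Share of variance explained: R² = p(1−p)s² / (1 + p(1−p)s²). Detectable d with the term = 0.479 × √(1−R²). Equivalent gain in women = 1/(1−R²) − 1.

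| s | R², p = 0.5 | Detectable d, p = 0.5 | Gain in women, p = 0.5 | Detectable d, p = 0.25 or 0.75 |
|---|---|---|---|---|
| 0.3 | 2.2% | 0.474 | 2% | 0.475 |
| 0.5 | 5.9% | 0.465 | 6% | 0.469 |
| 0.8 | 13.8% | 0.445 | 16% | 0.453 |

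Put as power: if 0.479 refers to the within-period SD, leaving the term out at p = 0.5 lowers 80% to 78.9%, 77.0% or 72.5%.

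**3. Two visits.** Suppose both Aim 1 visits fall in one period and 0.2 is the within-period correlation. The mean of two visits then has variance (1 + 0.2)/2 = 0.6, and the inflation at p = 0.5 is 1 + 0.25s²/0.6 = 1.038, 1.104 or 1.267. Power falls from 80% to 78.2%, 75.1% or 67.7%. The single-visit figures are therefore on the low side for such women.

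**4. Chance imbalance in Aim 1.** The SD of the resulting error in the arm difference is s × √(p(1−p) × 2/n). At p = 0.5 this is 0.021 for s = 0.3 and 0.035 for s = 0.5.

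**5. Aim 2A.** With 142 completers (71 per arm), a single-visit comparison without baseline adjustment has detectable d = 3.417 × √(2/71) = 0.574. A period term would bring it to 0.567, 0.556 or 0.533 for the three shifts at p = 0.5. This overstates the gain. A shift that is constant over a woman's postpartum visits goes into her random intercept and cancels from the Treatment × Time contrast. In the fallback main effect, the pregnancy value absorbs part of it when baseline and follow-up share a period.

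**6. Precision of a by-period report in Aim 1, p = 0.5.** Detectable difference between the two period-specific effects: (1.960 + 0.842) × √(8/101.65) = 0.79 SD at alpha 0.05, and 3.417 × √(8/101.65) = 0.96 SD at 0.01.

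**The case against.** The strongest reply is that nothing in the documents says period or mode affects mood, sleep or dropout, or how women divide between periods. Collecting a COVID questionnaire shows interest, not a known effect. In a randomised linear model an extra prognostic covariate is optional, and for shifts up to 0.5 SD the single-visit cost is about 3 power points or less. All of this stands, and it limits the point to an improvement.

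The objection on Aim 2A also stands for its primary interaction (step 5). It does not reach Aim 1, where only EPDS has a stated screening adjustment. Nor does the baseline argument reach infant outcomes, which have no pregnancy value. The open-ended moderators and the illustrative imbalance list leave room for period but do not pre-specify it.

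Three stronger readings are tempting and are not supported:
- **That a known prognostic shift is being ignored.** Its existence and size are assumptions here.
- **That the arm comparison is biased through dropout.** At p = 0.5, retention of 75% before and 60% during COVID in PREPP, reversed in ETAU, would give completers seen during COVID of 0.30/0.675 = 44% against 0.375/0.675 = 56%. With a 0.5 SD shift, that is 0.111 × 0.5 = 0.06 SD before any baseline adjustment. Nothing in the documents suggests such mirrored retention.
- **That by-period results would show whether PREPP works in person or virtually.** Period carries both mode and pandemic conditions. The Experimental Arm section says that timing sessions with medical visits will "enable us to test the feasibility of incorporating these sessions into routine medical care", but that concerns scheduling and does not say that virtual sessions lose the link.

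**Conclusion.** The omission is real and its consequence is minor. Four of the five scheduled mood-assessment sessions from the first prenatal visit onward switch mode with COVID, while no Aim 1 or Aim 2 model contains period and no by-period result is planned. The expected cost is a small loss of precision, mainly in Aim 1: about 2% to 16% of sample size for an assumed shift of 0.3 to 0.8 SD and a 50:50 split, and less with an uneven split. In Aim 2A it is smaller, except for women whose visits straddle the change, whose number is not given.

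One feature remains even with the term. Women seen entirely before COVID go in-person, phone, in-person across the postpartum visits, so mode is partly tied to Time. Both arms share this pattern, so it does not of itself bias the arm comparison.

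**What to change.** - Define one calendar cut-off date for the COVID period, set without reference to outcomes by arm, and record when it was set. The documents give no date.
- Add a fixed effect for the period of the visit to every Aim 1 and Aim 2 model. Take it from the visit date, not from the mode used, which could depend on arm.
- Report the numbers per arm and the PREPP-ETAU difference with its interval by period at randomisation. Label this descriptive, and state that it cannot separate mode from pandemic conditions.

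The cost is SAP wording and one degree of freedom per model, using visit dates. The document is dated November 2024 and describes some procedures in the past tense, so data collection may be well advanced. If outcomes by arm have already been seen, the change should be declared as made after that point.

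The by-period estimates will be too imprecise to support a claim of difference or of sameness, and should not decide anything in the analysis.
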